BNT162b2 COVID-19 vaccine has been administered to many millions of individuals (including 12 – 16 year-olds), and NVXCoV2373 has been administered to over 50000 participants in clinical trials, including over 1400 in adolescents. They therefore have a well-established safety profile. Specific concerns have been raised regarding a risk of myocarditis following a second dose of BNT162b2 in young males aged 12 to 17 years (9.8 per million first doses, rising to 67 per million after the second dose). Participants will be made aware of this at the time of enrolment and this will be specified in participant and parent information sheets. Participants will be advised to seek medical attention should they experience any of the cardinal symptoms of myocarditis (chest pain or pressure; palpitations; breathlessness after exercise, at rest or lying down; sweatiness). The diagnostic criteria for myocarditis are documented in Appendix D.(19)

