9.6.1.1.4. Vaccination at D0

Participants will be considered enrolled to the trial at the point of receipt of the first vaccine administered by the study team. All vaccines will be administered intramuscularly according to specific SOPs. The participant will stay in the trial site for observation for at least 15 minutes, in case of immediate adverse events. Participants will be issued with an NHS COVID-19 vaccination record card at the first immunisation with entry of “BNT162b2” and batch number. This will be updated at the second immunisation, but boost vaccine type or batch number will not be added as this would unblind participants; instead, “COVID-19 vaccine”, “Com-COV3 Trial” will be added. We will correspond with holders of the participant’s medical information records (e.g. GPs) to enable updating of these records.

9.6.1.1.5. eDiary

Participants/parents/guardians will be given an oral thermometer, tape measure and diary (electronic, but for those who are unable to use an electronic diary, a paper version will be made available), with instructions on use. All participants will be given the emergency 24-hour telephone number to contact the on-call study physician if needed. Participants/parents/guardians will be instructed on how to self-assess the severity of the solicited and unsolicited AEs they are entering in the diaries. There will also be space in the diary to self-document unsolicited AEs, and whether medication was taken to relieve the symptoms. It will also log any serious medical illnesses or hospital visits which may have occurred over the entire course of the study and any diagnosis of SARS-CoV-2 infection. Given the potential for physical exercise to raise troponin and NT-proBNP independently of myocardial inflammation, there will be a space in the diary to record episodes of strenuous physical activity (“defined as anything that makes you feel really out of breath”) in the period between the booster vaccine and the D70 visit. Participants/parents/guardians will be asked to report on solicited AEs for 7 days from prime and boost dose (and longer if symptoms persist at day 7, until resolution or stabilisation of symptoms) and unsolicited AEs for 28 days. The Diary will collect information on the timing and severity of the following solicited AEs:

Table 1 Solicited AEs collected on post vaccination diary cards

Com-COV3 Protocol

©Copyright: The University of Oxford

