Local solicited AEs	Pain, Tenderness, Redness, Warmth, Itch, Swelling, Induration
Systemic solicited AEs	Fever, Feverishness, Chills, Joint pains, Muscle pains, Fatigue, Headache, Malaise, Nausea, Vomiting, Diarrhoea

Post-vaccination (7 and 28 day) diary information will be reviewed by a clinician daily, and participants may be telephoned to discuss further, should there be any clinical concerns.

The diary will contain an instruction to contact the trial team by telephone should any encounter be a hospitalisation, or if they have concerns about their health.

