26. APPENDIX D: DEFINITION OF MYOCARDITIS

Brighton Collaboration criteria provide a clinical definition of myocarditis.(19) They distinguish definitive, probable and possible cases, as follows:

Definitive case:

Histopathologic examination of myocardial tissue (autopsy or endomyocardial biopsy) showed myocardial inflammation

OR Elevated myocardial biomarkers (troponin T and/or troponin I), **AND**

Abnormal Imaging Study EITHER

Abnormal Cardiac Magnetic Resonance Study (at least 1 of the findings below):

1. Oedema on T2 weighted study, typically patchy in nature
2. Late gadolinium enhancement on T1 weighted study with an increased enhancement ratio between myocardial and skeletal muscle typically involving at least one non-ischemic regional distribution with recover (myocyte injury)

OR Abnormal Echocardiogram (at least 1 of the findings below):

1. New focal or diffuse left or right ventricular function abnormalities (e.g. decreased ejection fraction)
2. Segmental wall motion abnormalities
3. Global systolic or diastolic function depression/abnormality
4. Ventricular dilation
5. Wall thickness change
6. Intracavitary thrombi

Probable case:

Clinical symptoms

EITHER Cardiac symptoms (at least 1 finding below):

1. Acute chest pain or pressure
2. Palpitations

3. Dyspnea after exercise, at rest, or lying down

4. Diaphoresis

5. Sudden death

OR Non-specific symptoms (at least 2 findings below):

1. Fatigue
2. Abdominal pain
3. Dizziness/syncope
4. Oedema
5. Cough

OR In infants and young children (at least two finding below):

1. Irritability
2. Vomiting
3. Poor feeding
4. Tachypnoea
5. Lethargy

AND Testing supporting diagnosis (Biomarkers, ECHO and ECG)

EITHER Elevated myocardial biomarkers (at least 1 finding below):

1. Troponin I
2. Troponin T
3. CK myocardial band

OR Echocardiogram (ECHO) abnormalities (at least 1 of the findings below):

1. New focal or diffuse left or right ventricular function abnormalities (e.g. decreased ejection fraction)
2. Segmental wall motion abnormalities
3. Global systolic or diastolic function depression/abnormality
4. Ventricular dilation

5. Wall thickness change
6. Intracavity thrombi

OR Electrocardiogram abnormalities that are new and/or normalise on recovery (at least 1 of the findings below):

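### None of the four cardinal myocarditis symptoms the protocol names is a solicited diary item, so the blinded participant's post-boost record does not prompt for them

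*Protocol*

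**What the plan says.** Protocol section 9.6.1.1.5 (eDiary), Table 1, fixes the solicited events. The local items are "Pain, Tenderness, Redness, Warmth, Itch, Swelling, Induration" and the systemic items are "Fever, Feverishness, Chills, Joint pains, Muscle pains, Fatigue, Headache, Malaise, Nausea, Vomiting, Diarrhoea". They are collected for 7 days after each dose, longer if symptoms persist. Anything else goes into a free-text space for unsolicited events, kept for 28 days.

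Section 5.2.1 singles out one cardiac risk: "Specific concerns have been raised regarding a risk of myocarditis following a second dose of BNT162b2 in young males aged 12 to 17 years". It lists the symptoms as "chest pain or pressure; palpitations; breathlessness after exercise, at rest or lying down; sweatiness", and what it does with them is this: "Participants will be advised to seek medical attention should they experience any of the cardinal symptoms of myocarditis".

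Sections 2 and 5 give myocarditis as a reason for studying alternatives to a full second dose, and section 5.1 offers a lower myocarditis risk as a possible benefit of the fractional dose. Appendix A schedules troponin and NT-proBNP at D56 and at D14 and D28 post boost, and at D0 for those primed in the study. The diary was adapted to help read these markers: "there will be a space in the diary to record episodes of strenuous physical activity".

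**The concern.** The diary is the trial's prompted symptom record. It is completed by a participant who does not know the allocation and is reviewed daily by a clinician. It asks about exercise, which can raise troponin innocently, but not about the symptoms that would make a raised troponin matter.

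A participant with mild chest discomfort or palpitations in the days after the boost has no item to tick. Whether the symptom is recorded then depends on someone writing it in as free text or recalling it at a later visit. Two things are at stake: a complete symptom record to set beside each post-boost cardiac marker, and a prompted, blinded symptom rate in the full-dose and one-third-dose arms, which are being compared partly because of this risk.

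**Working it through.** **1. Count.** Table 1 has 7 local + 11 systemic = 18 solicited items. Matched against the four symptom groups in section 5.2.1:

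| Symptom in 5.2.1 | Solicited in Table 1? |
|---|---|
| Chest pain or pressure | No (the local item on pain concerns the injection site) |
| Palpitations | No |
| Breathlessness | No |
| Sweating | No |

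Overlap: 0 of 4.

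**2. What Appendix D needs.** A definitive case rests on histology, or on raised troponin plus abnormal imaging, and needs no symptom. A probable case needs symptoms, supporting tests (a raised biomarker is enough) and no alternative diagnosis. So a raised troponin without imaging or histology can be classed as probable only if symptoms are known. The cardiac symptom list includes "Dyspnea after exercise, at rest, or lying down"; one finding suffices. The non-specific list has five entries and needs two; of these only fatigue is solicited, which is 1 of 5.

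**3. Timing.**
- Prompted diary: days 0-7 post boost.
- First post-boost visit: day 12-17, that is 12 − 7 = 5 to 17 − 7 = 10 days after the prompted week ends.
- Free-text diary: to day 28. The D28 visit window is day 28-42, so up to 42 − 28 = 14 days before the second marker sample may fall outside the diary.

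**4. Who asks, and what.** Under section 9.5 delivery staff know the arm, while the participant is blinded until the day 84 visit. Section 11.6.2 has AESIs actively solicited at each visit, but the cardiac entry in section 11.10 lists diagnoses (myocarditis, pericarditis, arrhythmias and others), not symptoms. Section 9.6.1.2 adds adverse-event assessment and an interim history, without stating a cardiac checklist. Section 17.4 recognises that knowing the allocation could influence diary completion.

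**5. Precision.** Section 12.1 gives ±4.5% for a 5% event rate with 90 per arm. Reproduced: 1.96 × √(0.05 × 0.95 / 90) = 0.045. That is the precision of one arm. For a difference with 5% in each arm: 1.96 × √(2 × 0.05 × 0.95 / 90) = 0.064, or ±6.4 points. The 5% is an assumed rate taken from a row of that table; the protocol gives no expected rate for these symptoms.

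**6. Case counts.** At 67 per million second doses (section 5.2.1, males aged 12 to 17), expected cases are 90 × 0.000067 = 0.006 per arm and 270 × 0.000067 = 0.018 overall. The chance of at least one case in 270 is about 1.8%, an upper illustration because the rate is for males only.

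**The case against.** The best case against is that the design is layered. Participants are told at enrolment which symptoms need attention. The diary takes free text for 28 days, logs hospital visits and tells families to telephone with concerns. Interim history, diary review and an SAE/AESI check are scheduled at D14 and D28 post boost, the same visits at which the cardiac markers are drawn. Which symptoms to prompt daily is a matter of choice, and cardiac markers are only an exploratory objective.

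Much of this stands. A reader might infer that cardiac symptoms are captured only if volunteered. The documents do not support that, because visit enquiry and active AESI solicitation are real routes. Nor do they support the inference that a raised troponin could not be interpreted at all, or that a blank free-text field would be taken as absence of symptoms; no section says so.

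What the objection does not supply is a prompted record from the blinded participant in the first week. The visit routes start at day 12-17, are run by staff who know the arm, and are framed around diagnoses or general enquiry. Advice to seek care is a safety instruction and yields no denominator.

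A second objection also stands: adding the items to the Table 1 systemic list would alter the primary outcome, which section 6 defines as solicited systemic reactions over 7 days. The remedy must avoid that.

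**Conclusion.** The point holds as a weakness in data capture that should be corrected. It is not a contradiction or a numerical error. None of the four cardinal symptoms is solicited; in the diary they rest on free text, and elsewhere on visit enquiry that begins at day 12-17 post boost and is not described as a symptom checklist. First-week symptoms that bear on a raised troponin under Appendix D are therefore not systematically recorded by the blinded participant. No analysis plan can recover this afterwards, because the protocol itself fixes the list.

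The gain from correcting it is modest. The data would be descriptive, and at an assumed 5% rate the between-arm uncertainty (±6.4 points) is larger than the rate itself. It would be wrong to read the point as saying that the trial could measure myocarditis risk with a better diary; about 0.02 expected cases in 270 rules that out. These precision figures assume 90 per arm, the planning figure in section 12.1; final arm sizes may differ after the change to 1:1 randomisation.

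**What to change.** - Add chest pain or pressure, palpitations, breathlessness and unusual sweating to the post-boost diary as a separate cardiac-symptom block. State that the block lies outside the solicited systemic reactions of Table 1, so the primary outcome is unchanged.
- Keep the block open until the D28 post-boost visit (window day 28-42), or repeat it at that visit. If it is repeated there, have it completed before the participant is told the allocation, since the day 84 visit in section 9.5 is 28 days after a day-56 boost (56 + 28 = 84).
- Report the items descriptively by arm, and list them beside any raised troponin or NT-proBNP value.

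Cost: four tick items in an existing e-diary and a short protocol amendment. Some non-specific positive answers will lead to follow-up calls. Participants boosted before the change will lack the items; their number should be reported by arm, and they should be left out of the denominators rather than counted as symptom-free. The change concerns data capture only and touches no dose, schedule or clinical rule.

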9.6.1.1.6. Safety pause

Given that a) the homologous BNT162b2 vaccine schedule is licensed for use in 12 to 16 year-olds, b) Data from COMCOV2 demonstrates that BNT162b2 prime followed by NVXCoV2373 boost is no more reactogenic than homologous BNT162b2/BNT162b2 and c) employing fractional dose vaccines as the boost dose are expected to be less reactogenic than full dose regimens, there will be no planned safety pause or expedited review of reactogenicity data. Should significant safety concerns arise at any point (e.g. an AESI) then the DSMB will be consulted as appropriate.

9.6.1.2.

Subsequent visits

Follow-up visits will take place as per the schedule of attendances described in APPENDIX A: SCHEDULE OF PROCEDURES. Participants will be assessed for local and systemic adverse events, interim history, review of diaries (paper or electronic) and blood, saliva/ nasal fluid sampling performed at these time points as detailed in the schedule of attendances. Observations and physical exam will be performed as and when clinically indicated.

Vaccination procedures will be as for D0 visit, adapted to the specific vaccine being administered as outlined in the clinical study plan. Scheduling of the second vaccination visit (D56) should be mindful of any planned routine non-COVID-19 immunisation outside the study (e.g. seasonal influenza vaccine), to avoid administration of the study COVID-19 vaccine within a period 7 days before or after the planned routine vaccine. If necessary, in this situation scheduling of the D56 visit can be delayed beyond the specified D56 study window, but must not be brought forward to less than 8 weeks following D0.

If participants experience adverse events which the investigator (physician), CI and/or DSMB chair deem to require further close observation, the participant may be admitted to an NHS

hospital for observation and further medical management under the care of the Consultant on call.

9.6.2. Visits for participants receiving their first dose of COVID-19 vaccine in the community

The screening visit for these participants will include all the procedures for informed consent and eligibility assessment described above (section 9.6.1.1.1 and 9.6.1.1.2) including date of first dose of COVID-19 vaccination in the community.

The screening visit may be combined with the D56 visit, or be scheduled to occur separately, at some time before the D56 visit.

At the D56 visit blood samples will be taken (as will nasal fluid and saliva samples, if consent has been given for this); booster vaccine will be determined by randomisation and administered; an e-diary will be supplied. These procedures will occur in the same way as described for those participants receiving their first dose of COVID-19 vaccine in the study.

Visits after D56 (i.e. D 14, 28, 132, 236 post boost), will involve the same procedures for all participants, whether or not they received their first dose of COVID-19 vaccine in the study or community. These are described in APPENDIX A: SCHEDULE OF PROCEDURES.

9.6.3. Participants under quarantine

Given the evolving epidemiological situation both globally and in the UK, should a participant be unable to attend any of their scheduled or unscheduled visits, a telephone consultation will be arranged in order to obtain core study data where possible. Participants should not attend for in-person visits if they are in their period of self-isolation/quarantine.

9.6.4. Admission of participants to hospital with COVID-19 infection

With the participant's/parent's/guardian's consent, the study team will request relevant sections of medical notes on any COVID-19 episodes resulting in hospitalisation. Any data which are relevant to assessing for disease enhancement will be collected. These are likely to include, but not limited to, information on ICU admissions, clinical parameters such as oxygen saturation, respiratory rates and vital signs, need for oxygen therapy, need for ventilatory support, imaging and blood tests results, amongst others.

9.7. Sample handling

Please refer to APPENDIX C: BLOOD SAMPLING for schedule of frequency and volume of blood sampling.

9.7.1. Sample handling for trial purposes

Immunogenicity will be assessed by a variety of immunological assays. This will include antibodies to SARS-CoV-Spike and non-Spike antigens by ELISA, ex vivo ELISpot assays for interferon gamma secreting T cell assays, and (potentially) neutralising and other functional antibody assays. Other exploratory immunological assays including cytokine analysis and other antibody assays, DNA analysis of genetic polymorphisms potentially relevant to vaccine immunogenicity and gene expression studies amongst others may be performed at the discretion of the Investigators.

Collaboration with other specialist laboratories in the UK, Europe and outside of Europe for further exploratory tests may occur. This would involve the transfer of serum, plasma, PBMC and/or other study samples to these laboratories, but these would remain anonymised. The analyses and which laboratories carry these out will be specified in the laboratory analysis plan.

Participants will be informed that there may be leftover samples of their blood (after all testing for this study is completed), and that such samples may be stored indefinitely for possible future research (exploratory immunology), including genotypic testing of genetic polymorphisms potentially relevant to vaccine immunogenicity. Participants will be able to decide if they will permit such future use of any leftover samples. With the participant's informed consent, any leftover cells and serum/plasma will be frozen indefinitely for future analysis of COVID-19 and other coronaviruses related diseases or vaccine-related responses. If a participant elects not to permit this, all of that participant's leftover samples will be discarded at the end of the trial.

Samples that are to be stored for future research will be transferred to the OVC Biobank (REC 21/SC/0161). If the participant/parent/legal guardian (as applicable) does not consent to storage in the Oxford Vaccine Centre Biobank, then all samples will be destroyed at the end of the study.

9.7.1.1. Nasal fluid & saliva samples

An exploratory analysis of mucosal immunity will be conducted at some sites using nasal fluid collected at V1, V2 and V3 using SAM-strips (synthetic absorptive matrix) and saliva samples. Analysis will be conducted initially with IgA and IgG ELISAs, with further exploratory immunology assays conducted based on results – more detail will be included in the laboratory analysis plan.

The same statements regarding collaboration, storage and use of samples as for blood in Section 0 apply here.

9.7.1.2. Sample handling for markers of cardiac stress

These will be centrifuged and frozen at sites before shipping to a central NHS laboratory, and tested for troponin and NT-proBNP. Residual samples will then be destroyed in accordance with standard NHS processes.

9.7.2. Sample handling for pregnancy testing

Urinary pregnancy testing: For female participants urine will be tested for beta-human chorionic gonadotrophin (β -HCG) immediately prior to vaccination. This will be a point of care test and no sample will be stored.

9.8. Early discontinuation/Withdrawal of participants

In accordance with the principles of the current revision of the Declaration of Helsinki and any other applicable regulations, a participant has the right to withdraw from the study at any time and for any reason, and is not obliged to give his or her reasons for doing so. The Investigator may withdraw the participant at any time in the interests of the participants' health and well-being. In addition, the participant may withdraw/be withdrawn for any of the following reasons:

- Administrative decision by the Investigator
- Ineligibility (either arising during the study or retrospectively, having been overlooked at screening).
- Significant protocol deviation
- Participant non-compliance with study requirements
- An AE, which requires discontinuation of the study involvement or results in inability to continue to comply with study procedures

The reason for withdrawal will be recorded in the CRF. If withdrawal is due to an AE, appropriate follow-up visits or medical care will be arranged, with the agreement of the volunteer, until the AE has resolved, stabilised or a non-trial related causality has been assigned. The DSMB or DSMB chair may recommend withdrawal of participants.

If the participant chooses to withdraw after receipt of the first dose of vaccine, they will not need to be formally unblinded, as they will all have received BNT162b2. If they withdraw after the second dose of vaccine, they will not be unblinded, unless criteria as described in 9.5 are met. since at present there is no recommendation for routine second dose in the age group being studied.

If a participant withdraws from the study, storage of samples will continue unless the participant specifically requests otherwise. Any data collected before their withdrawal will still be used in the analysis for safety and trial integrity; if the participant requests this could be de-identified following the end of the study.

In cases of participant withdrawal, long-term safety data collection, including some procedures such as safety bloods, may continue as appropriate if participants have received any vaccine doses through the trial, unless they decline any further follow-up.

